6.12 Definition and management of on-treatment hepatitis flares

On-treatment hepatitis flare is defined as increase in ALT to ≥ 300 U/L for men and ≥ 200 U/L for women AND > 3 times baseline (day 0) value. Participants who meet criteria of a flare will be seen every 4 weeks until ALT decreases to < 300 U/L for men and < 200 U/L for women. Severe on-treatment hepatitis flare is defined as ALT ≥ 1000 U/L regardless

of gender. Participants who meet criteria of a severe flare will be seen every week until ALT decreases to <1000 U/L, at which point they will be evaluated every 4 weeks until ALT <300 U/L for men and <200 U/L for women and thereafter at scheduled visits per study protocol. Participants who experience hepatitis flares may continue treatment if total bilirubin is <2.0 mg/dL and direct bilirubin <1.0 mg/dL. Participants who experience severe hepatitis flares may continue treatment at the discretion of the investigator if total bilirubin is <2.0 mg/dL and direct bilirubin <1.0 mg/dL.

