6.13. End-of-treatment (prior to week 192) assessment

6.13.1. Eligibility criteria for discontinuation of treatment prior to week 192

Participants who meet either of the criteria below will be discontinued from treatment:

- Grade IV toxicity (laboratory or clinical)
- Hepatic decompensation while on peginterferon defined by:
 - Total bilirubin ≥2.0 mg/dL and direct bilirubin ≥1.0 mg/dL
 - Any clinical decompensation
- Participant refuses to continue treatment/participation in study

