6.13.2. End of treatment assessment

Participants who stop treatment early will complete assessments specified for the week 192 visit (see section 6.5 and Appendix 3).

Participants who discontinue treatment due to Grade IV toxicity or hepatic decompensation will continue to be followed until these events are resolved or stabilized, according to the post-treatment follow-up schedule.

6.13.3. Follow-up visit schedule after week 192

All participants who are eligible to stop treatment at week 192 will be seen at weeks 196, 200, 204, 208, 212, 216, 228, and 240 (corresponding to weeks 4, 8, 12, 16, 20, 24, 36, and 48 post-treatment for those whose treatment is discontinued). This is the minimal follow up required. Laboratory testing (liver panel) plus telephone assessment can replace an outpatient visit at weeks 208 and 212 if ALT at the preceding assessment (week 204 and week 208, respectively) is <300 U/L for men or <200 U/L for women and bilirubin is normal (total bilirubin <1.5 mg/dL or direct bilirubin <0.5 mg/dL). Additional visits for safety monitoring should be included as needed. Participants who are not eligible to stop treatment at week 192 and who remain on treatment will be seen at weeks 204, 216, 228 and 240 (i.e., 12, 24, 36 and 48 weeks after week 192).

Laboratory testing will be performed as outlined in Appendix 4. Blood samples for serum/plasma will be collected at each outpatient visit.

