7.1. Criteria for permanent and premature discontinuation of treatment

- Death
- Grade IV toxicity (laboratory or clinical)
- Hepatic decompensation defined by:
 - Total bilirubin ≥ 2.0 mg/dL and direct bilirubin ≥ 1.0 mg/dL
 - Any clinical decompensation

7.2.a. Adverse effects of peginterferon alfa-2a

Common side effects of peginterferon alfa-2a include influenza-like symptoms, particularly with the first few injections, fatigue, neuropsychiatric symptoms such as depression and reduction in white blood cell counts and platelet counts. Hyper- or hypothyroidism has been noted to occur in up to 5% of participants receiving peginterferon alfa-2a.

Some rare but potentially serious side effects include:

- neuropsychiatric complications, which may include suicide, suicidal ideation, acute psychosis and severe depression
- serious and severe bacterial infections; fatal infections have been reported during treatment with peginterferon alfa-2a
- pancreatitis
- interstitial pneumonitis, fatal cases have been reported with peginterferon alfa 2a use

Other possible but uncommon adverse events associated with peginterferon alfa-2a include:

- development or exacerbation of existing autoimmune disorders such as rheumatoid arthritis, systemic lupus erythematosus, idiopathic thrombocytopenic purpura, hemolytic anemia, type 1 diabetes, psoriasis, etc.
- pulmonary disorders including dyspnea, pulmonary infiltrates, and sarcoidosis
- exacerbations of inflammatory bowel disease
- eye disorders, including decrease or loss of vision, retinal hemorrhages
- hearing disorders, including loss of hearing and tinnitus
- hypersensitivity reactions including severe skin reactions, in the spectrum of Stevens Johnson syndrome

7.2.b. Peginterferon alfa-2a dose reductions

Factors that will lead to a reduction in the dose of peginterferon alfa-2a include:

1. Disabling symptoms, which, in the opinion of the study physician, are related to peginterferon alfa-2a treatment and prevent the participant from performing his/her occupation or daily tasks.
2. A rash consistent with allergic reaction or vasculitis.
3. Reductions in the neutrophil count according to the guidelines in Appendix 2.
4. A reduction in platelet count according to the guidelines in Appendix 2.
5. Any adverse reaction, which, in the opinion of the study physician, places the participant at increased risk of a serious adverse effect.

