The dose of study medications may be decreased due to adverse events or laboratory abnormalities. The weekly dose of peginterferon alfa-2a will be reduced in graduated steps as follows:

- Level 1 decrease from 180 µg to 135 µg
- Level 2 decrease from 135 µg to 90 µg
- Level 3 decrease from 90 µg to 45µg

For participants who require a downward dose adjustment for neutropenia or thrombocytopenia, laboratory values should be repeated, if practical, prior to the next dose of peginterferon alfa-2a to confirm the result and dictate the course of action. Participants who remain with a neutrophil count below 500/mm³ (but above 250/mm³) or a platelet count below 50,000/mm³ (but above 25,000/mm³) should receive stepwise dose reductions until levels of neutrophils and platelets are $\geq 500/\text{mm}^3$ or 50,000/mm³, respectively, or until a dose of 45 µg of peginterferon alfa-2a is reached. Participants who have a neutrophil count below 250/mm³ or a platelet count below 25,000/mm³ should have their peginterferon alfa-2a dose held. Peginterferon alfa-2a may be resumed at the previous reduced dose when the neutrophil count has been above 500/mm³ or platelet count above 50,000/mm³ on 2 occasions at least 1 week apart.

7.2.c. Guidelines for subsequent peginterferon alfa-2a dose adjustments

Once a participant's dose has been decreased for laboratory abnormalities or adverse events, the study physician may attempt to increase the dose back to or toward the previous stable level only if the following conditions are satisfied:

1. The event or circumstance responsible for the dosage adjustment has resolved or improved;
2. The participant has been at the lower dose for ≤ 4 consecutive doses;
3. The participant had ≤ 6 total doses administered at the lower level during the entirety of the treatment period.

If four or more consecutive doses of peginterferon alfa-2a are held or otherwise not administered (i.e., the participant has not received test medication for more than 28 days), the participant will be considered intolerant of the test medication or non-compliant, whichever is more appropriate to the clinical situation. In such cases, the study physician will discontinue peginterferon alfa-2a but tenofovir DF treatment will continue.

Every attempt will be made to keep those participants randomized to treatment with peginterferon alfa-2a on therapy by dose reduction. The use of hematological growth factors during the study will not be allowed.

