7.2.d. Screening and management for depression

The CES-D will be used, along with the study physician's judgment, to screen participants for depression at the screening visit (8 weeks prior to randomization) and to monitor for onset or worsening of symptoms during the treatment.

Screening Visit (8 weeks prior to randomization): If the participant has a CES-D score >15 at the screening visit (8 weeks prior to randomization), clearance from a mental health provider may be considered at the discretion of the study physician. In addition to clarifying possible psychiatric disorders, the mental health provider may advise on the need for adjuvant medical or counseling therapy and suitability for enrollment.

During treatment: Potential mood disturbance/medication intolerance will be assessed at each visit by study personnel. The CES-D will be administered every 12 weeks for 48 weeks. If the participant has a score >15, the study physician will determine whether referral to a mental health provider is indicated. If the participant has a score of at least 27, the study physician will refer to a mental health provider for evaluation and management. Any participant who develops recurrent suicidal ideation, a suicide plan and/ or makes a suicide attempt should have peginterferon alfa-2a immediately discontinued and be referred to a mental health provider for further management.

Suggested guidelines for peginterferon alfa-2a dose reduction:

- Unpleasant and/or disabling side effects might prompt dose reduction, but this is not required.
- A CES-D score of 16-26 might prompt further consideration of dose reduction, but is not a requirement for dose reduction.
- A score of at least 27 should prompt attention from the PI and dose reduction or discontinuation be considered.

If the management of the depression is not successful after eight weeks or if the participant develops suicidal or homicidal ideation, the peginterferon alfa-2a will be stopped but tenofovir DF continued until the end of the treatment period. The participant will be referred to a mental health provider.

7.3.a. Adverse effects of tenofovir DF

All nucleoside and nucleotide analogues carry a warning about the risk of lactic acidosis and severe hepatomegaly and steatosis because of the possibility of mitochondrial injury.

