Serum calcium, phosphate and creatinine levels will be monitored. Serum vitamin D levels will be measured at baseline and supplements prescribed for the participants as clinically indicated. Participants will have bone densitometry done prior to initiating therapy if clinically indicated (as standard of care). If either osteopenia or osteoporosis is present on the bone densitometry done prior to initiation of treatment, the participant can be enrolled as long as he/she is concurrently treated for osteopenia or osteoporosis. Repeat bone densitometry may be performed if clinically indicated (as standard of care).

7.3.d. Discontinuation of tenofovir DF for selected biochemical abnormalities

Tenofovir DF will be permanently discontinued and the participant considered a treatment failure for Grade 3 hypophosphatemia (1.0-1.4 mg/dL) that does not correct within 2 weeks with phosphate supplements or Grade 4 hypophosphatemia (<1.0 mg/dL) or otherwise unexplained serum creatinine elevations by ≥ 1.2 mg/dL and ≥ 0.5 mg/dL above baseline on two consecutive occasions or calculated creatinine clearance <30 ml/min that develop on therapy. For lesser degrees of renal insufficiency not requiring discontinuation, the dose of tenofovir DF will be adjusted according to the manufacturer's recommendation.

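### Sections 7.1 and 6.13.1 stop an unnamed treatment for any Grade IV laboratory toxicity, in conflict with the flare rule in 6.12 and the peginterferon hold rule in 7.2.b

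*Combined protocol and SAP*

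**What the plan says.** **The general rule.** Section 7.1, whose heading speaks of permanent and premature discontinuation, lists "Grade IV toxicity (laboratory or clinical" with no drug, attribution or confirmation attached. Section 6.13.1 repeats the trigger and makes it binding: "Participants who meet either of the criteria below will be discontinued from treatment". The only reference to peginterferon in that list belongs to the hepatic decompensation item. Section 6.13.2 then places these participants in follow-up: "Participants who discontinue treatment due to Grade IV toxicity or hepatic decompensation will continue to be followed until these events are resolved".

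**The specific rules.**
- Section 6.12, on-treatment flares: treatment may go on if bilirubin is low. For ALT ≥1000 U/L, participants with "severe hepatitis flares may continue treatment at the discretion of the investigator if total bilirubin is <2.0 mg/dL and direct bilirubin <1.0 mg/dL".
- Text under 7.2.b, neutrophils <250/mm³ or platelets <25,000/mm³: participants "should have their peginterferon alfa-2a dose held. Peginterferon alfa-2a may be resumed at the previous reduced dose" once counts recover.
- Section 7.2.c, four or more consecutive peginterferon doses missed: "the study physician will discontinue peginterferon alfa-2a but tenofovir DF treatment will continue".
- Section 7.2.d, depression not controlled or suicidal or homicidal ideation: "the peginterferon alfa-2a will be stopped but tenofovir DF continued until the end of the treatment period".
- Section 7.3.d, phosphate and renal abnormalities: "Tenofovir DF will be permanently discontinued and the participant considered a treatment failure for Grade 3 hypophosphatemia" that does not correct within 2 weeks, and also for phosphate <1.0 mg/dL (Grade 4) and for defined creatinine or creatinine clearance changes.

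Appendix 2 tells sites to stop the drug at the same two count thresholds for which 7.2.b says hold. Section 7.6.1 grades severity by the NCI criteria. The version and the Grade IV cut-offs for ALT, neutrophils and platelets are not given.

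**The concern.** Arm B takes two drugs and arm A takes one, so an instruction to stop treatment means different things depending on which drug is meant. Elsewhere the plan separates them with care: 7.2.c and 7.2.d end peginterferon and keep tenofovir DF, and 7.3.d names tenofovir DF and gives the laboratory value when that is the drug to stop. Sections 7.1 and 6.13.1 do neither.

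The stake is mainly safety. Section 7.3.a notes the class warning about exacerbation of hepatitis when anti-HBV agents are withdrawn. At week 192 the plan allows withdrawal only if all eight criteria of 6.5.1 are met, including no cirrhosis on the baseline biopsy and 24 weeks of HBV DNA <1000 IU/mL. A literal 7.1 stop has no such screen. It could remove tenofovir DF from a viraemic or cirrhotic participant because of a blood count of the kind expected with peginterferon.

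There is also a smaller analysis stake. Secondary endpoint 2.2.8 is the rate of discontinuation due to adverse events. The same low count is a permanent stop under 7.1 and a temporary hold of one drug under 7.2.b, so the rate could depend on which section a site follows.

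**Working it through.** The plan gives no figure on this point to reproduce, so the check compares the rules.

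| Event | 7.1 and 6.13.1, if Grade IV | Specific rule |
|---|---|---|
| ALT ≥300 U/L (men) or ≥200 U/L (women) and >3 times baseline, low bilirubin | Stop treatment | 6.12: may continue |
| ALT ≥1000 U/L, low bilirubin | Stop treatment | 6.12: may continue, investigator's discretion |
| Neutrophils <250/mm³ or platelets <25,000/mm³ | Stop treatment | 7.2.b: hold peginterferon, may resume |
| Phosphate <1.0 mg/dL | Stop treatment | 7.3.d: stop tenofovir DF permanently |

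The last row shows no conflict over tenofovir DF. The first three rows conflict only where a value is also Grade IV.

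**Do the rules overlap when the cut-offs are unknown?** Assume only that the grading scale puts Grade IV beyond some cut-off for each test: ALT above *a*, neutrophils below *c*, platelets below *p*.
1. ALT: 6.12 sets no upper limit. With low bilirubin, every ALT that is above *a* and also meets the flare definition falls under both rules.
2. Neutrophils: the hold rule sets no lower limit. Every count below the smaller of *c* and 250/mm³ falls under both rules.
3. Platelets: likewise, every count below the smaller of *p* and 25,000/mm³.

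None of these regions is empty, whatever *a*, *c* and *p* are. The cut-offs decide how wide the overlap is, not whether it exists. Whether Grade IV also reaches the step-down bands (neutrophils 250 to 500/mm³, platelets 25,000 to 50,000/mm³) cannot be told from the documents.

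**Is there a precedence rule?** None was found. Appendix 2 allows other physician responses, but only to its own peginterferon guidelines. Section 9.1 refers to Section 7 for toxicity, dose adjustment and discontinuation without ranking its parts.

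**What happens to tenofovir DF?** Under 7.2.b a cytopenia changes only the peginterferon dose. If the hold lasts four or more doses, 7.2.c ends peginterferon and expressly continues tenofovir DF. Under 7.1 read literally, the same participant loses both drugs permanently.

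**Appendix 2 against 7.2.b.** At identical thresholds one says stop and the other says hold and allows resumption. The Appendix 2 column heading also covers delays in dosing, so the entry can be read as a hold, but the wording does not match.

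**The case against.** The best reply is that no site is forced to break a rule. Section 6.12 permits continuation but does not require it, so stopping complies with 6.12 and 7.1 together. Resumption under 7.2.b is also optional. That is right, and a reader who infers that sites cannot comply with both rules goes too far. But the reply works only if every site applies the stricter general rule and takes the unnamed treatment to include tenofovir DF, which is the outcome the specific rules avoid.

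The triggers in 7.2.c and 7.2.d are missed doses and psychiatric events, not Grade IV laboratory values. They show how the plan separates the drugs; they are not further conflicts.

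Intent can also be argued. Section 7.2.c wants participants kept on peginterferon by dose reduction, and the Appendix 2 general table answers life-threatening events by stopping the drug in a peginterferon-only table. Sites may therefore follow the specific rules. This supports the repair but does not replace it.

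A reader might infer that one ALT >1000 U/L with HBV DNA ≥10,000 IU/mL orders both a stop (7.1) and a restart (6.14.2). It does not: 6.14.2 governs participants already off drug, and 7.1 those on it.

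Harm is limited. Those who stop early for an adverse event follow the Appendix 4 schedule. Section 6.14.2 can restart tenofovir DF, although none of its seven criteria is recovery of the toxicity. Section 5.6 bars other anti-HBV drugs only while study drugs are taken, and 7.3.b recommends alternative therapy after renal or phosphate discontinuations. Weeks off study tenofovir DF are therefore not necessarily untreated weeks.

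**Conclusion.** The point holds as an unresolved conflict between a general stopping rule and two specific rules. The general rule, followed as written, permanently withdraws tenofovir DF for ALT flares or cytopenias that the specific rules manage without stopping it. This rests on the printed text and on one assumption: that the grading scale has a Grade IV level for ALT, neutrophils and platelets.

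Its size cannot be stated as a count or as weeks of lost treatment. A reader might turn to the 10% Grade IV stopping rule in 9.1, but that limits all Grade IV toxicity and counts no conflicts. Nor can a maximum time off drug be taken from the visit schedule, because 6.4 allows unscheduled visits and 6.14.2 allows restart. A reader might also infer damage to the primary result. The documents do not support that: the intention-to-treat comparison, sample size and power are unaffected. What remains is an avoidable safety ambiguity, possible site variation in 2.2.8, and a minor mismatch in Appendix 2.

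**What to change.** In 7.1 and 6.13.1, name the drug or drugs to be stopped and state that:
- Grade IV toxicity attributed to peginterferon, including cytopenias managed under 7.2.b and Appendix 2, stops or holds peginterferon only, and tenofovir DF continues;
- ALT flares are governed by 6.12;
- tenofovir DF is stopped under 7.3.b and 7.3.d, or for Grade IV toxicity attributed to it.

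In Appendix 2, for neutrophils <250/mm³ or platelets <25,000/mm³, replace the stop instruction with: *Hold; resume per 7.2.b; discontinue peginterferon if four or more consecutive doses are held (7.2.c)*.

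The cost is wording in three places, with no new data, visits or participants. There is a small downside: severe flares with low bilirubin stay at the investigator's discretion instead of a mandatory stop, as 6.12 already provides. If the sponsor wants the mandatory stop, 6.12 should say so. Where the affected treatment period has already passed, the sponsor can instead document how sites applied 7.1 before analysing 2.2.8.

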2.2.3. Sustained off treatment (36 and 48 weeks after end of treatment) responses

- a. ALT \leq 38 U/L (males), \leq 25 U/L (females) corresponding to approximately 1.25 xULN.
- b. HBV DNA $<$ 1000 IU/mL.
- c. HBV DNA $<$ 1000 IU/mL AND ALT \leq 38 U/L (males), \leq 25 U/L (females) corresponding to approximately 1.25 xULN.
- d. HBV DNA $<$ 20 IU/mL (LLOQ of COBAS Ampliprep/COBAS TaqMan HBV v2.0 test).

2.2.4. Sustained off treatment (36 and 48 weeks after end of treatment) responses in participants with low end of treatment HBsAg levels ($<$ 2000 IU/mL) versus participants with high end of treatment HBsAg levels (\geq 2000 IU/mL)

- a. Cumulative HBsAg loss.
- b. HBeAg loss.
- c. HBsAg seroconversion.
- d. HBeAg seroconversion.
- e. ALT normalization (males \leq 30 U/L, females \leq 20 U/L).
- f. HBV DNA $<$ 1000 IU/mL.
- g. HBV DNA $<$ 20 IU/mL (LLOQ of COBAS Ampliprep/COBAS TaqMan HBV v2.0 test).

2.2.5. Sustained off-treatment (36 and 48 weeks after end of treatment) responses in participants with a substantial drop of HBsAg levels (\geq 1 log from baseline to end of treatment) versus participants who did not have substantial drop of HBsAg levels ($<$ 1 log from baseline to end of treatment)

- a. Cumulative HBsAg loss.
- b. HBeAg loss.
- c. HBsAg seroconversion.
- d. HBeAg seroconversion.
- e. ALT normalization (males \leq 30 U/L, females \leq 20 U/L).
- f. HBV DNA $<$ 1000 IU/mL.
- g. HBV DNA $<$ 20 IU/mL (LLOQ of COBAS Ampliprep/COBAS TaqMan HBV v2.0 test).

2.2.6. Sustained off-treatment (36 and 48 weeks after end-off treatment) responses in participants with end of treatment HBsAg level $<$ 2000 IU/mL and HBV DNA below 1000 IU/mL versus participants with end of treatment HBsAg levels \geq 2000 IU/mL and HBV DNA \geq 1000 IU/mL

- a. Cumulative HBsAg loss.
- b. HBeAg loss.

- c. HBsAg seroconversion.
- d. HBeAg seroconversion.
- e. ALT normalization (males \leq 30 U/L, females \leq 20 U/L).
- f. HBV DNA $<$ 1000 IU/mL.
- g. HBV DNA $<$ 20 IU/mL (LLOQ of COBAS Ampliprep/COBAS TaqMan HBV v2.0 test).

2.2.7. Treatment failure- Cumulative rates of primary nonresponse, partial virologic response and confirmed virologic breakthrough

2.2.8. Rate of discontinuation of treatment due to adverse events.

2.2.9. Rates of adverse events and serious adverse events.

3. Study design

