Tenofovir DF has been associated with instances of lactic acidosis, but only in participants receiving other medications that have been associated with this complication, such as didanosine, stavudine and zidovudine. It is not clear whether tenofovir DF when used by itself or in combination with peginterferon alfa-2a, is associated with mitochondrial toxicity either to the liver (lactic acidosis, acute fatty liver and hepatic failure), muscle (myositis), nerves (neuropathy) or pancreas (acute pancreatitis).

In addition, all agents with activity against HBV replication carry a warning label about the risk of exacerbation of hepatitis after discontinuation of treatment. This issue is addressed by the protocol design and close follow-up of participants after stopping therapy (see section 6.6, 6.14.1, and Appendix 4).

7.3.b. Tenofovir DF and renal function

Tenofovir DF is principally eliminated by the kidney. Renal impairment, including cases of acute renal failure and a Fanconi-like syndrome (proximal renal tubular dysfunction with severe hypophosphatemia), has been reported.

Adverse Event Monitoring and Management Related to Elevated Serum Creatinine (Cr)
Nephrotoxicity will be based upon serum creatinine results:

- If Cr \geq 0.5 mg/dL above baseline, repeat testing within 72 hrs will be performed and drug continued unless the study physician considers drug discontinuation necessary.
- If Cr increases to \geq 1.2 mg/dL and by \geq 0.3 mg/dL from baseline, additional testing at the next scheduled visit should be considered (see Manual of Operations). If Cr \geq 1.2 mg/dL and $>$ 0.5 mg/dL above baseline on two consecutive occasions, the study drugs will be discontinued and not restarted unless another, reversible cause of creatinine elevations is identified. If the study physician identifies an alternative cause for the increase in Cr, study drugs may be resumed at discretion of study physician if calculated Cr clearance is $>$ 30 ml/min with tenofovir DF dose adjustment.
- Any study participant discontinued from the study will be recommended to commence anti-HBV therapy with an alternative HBV drug immediately (this drug will not be provided by the study).

Tenofovir DF Dosing is Based Upon Creatinine Clearance (CrCL)

Creatinine clearance will be calculated in all participants prior to initiating therapy and at each study visit to determine tenofovir DF dose.

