Recruitment Retention Protocol adherence(e.g., meeting inclusion/exclusion criteria, treatment compliance) Pregnancy and outcomes in female participants	Quarterly reports for NIDDK and the appropriate oversight committees
Adverse events and Serious Adverse Events (SAE) that do not meet expedited reporting criteria	Quarterly reports for NIDDK and the appropriate oversight committees
Serious Adverse Events that meet expedited reporting criteria*	As they occur for NIDDK, DSMB, appropriate industry partner(s), and

	cumulative reports quarterly
Laboratory data	Yearly for the DSMB

The definition of adverse and serious adverse events is provided in section 7.6.1 of this protocol along with the reporting procedures in the MOP.

Stopping rules during the treatment phase (up to Week 192)

No interim analysis for efficacy is planned for this clinical trial, since the primary endpoint is expected to occur very rarely during the treatment period. As mentioned above, adverse event reporting will be quarterly throughout the study. Additional analyses will be performed at the recommendation of the DSMB if there are any concerns raised by adverse events or serious adverse events reported. The following study-wide stopping rules have been agreed upon by the clinical investigators for this interim analysis. The study will be stopped if at least one of the following occurs:

1. If the incidence of renal toxicity (defined as a persistent increase in serum creatinine >1.0 mg/dL above baseline on two successive visits 4 weeks apart or persistent grade 3 or grade 4 hypophosphatemia (requiring TDF discontinuation) exceeds 10% in either of the two study arms.
2. If the incidence of peripheral neuropathy (documented by EMG) exceeds 10%.
3. If the incidence of grade IV toxicity exceeds 10% in either of the two study arms.

Stopping rules during treatment discontinuation phase (Weeks 192 to 240)

The following has been agreed upon by the clinical investigators

1. If more than 1 participant develops clinical decompensation, no further participants will undergo treatment withdrawal until the formal review by investigators and the DSMB
2. Resumption of treatment withdrawal may occur if the DSMB and investigators determine the safety measures are adequate AND that the benefits of continued study of treatment withdrawal outweighs the risks

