Appendix 4: Time and event chart after week 192 or treatment discontinuation *

Weeks Post Treatment Discontinuation	4	8	12	16 ⁵	20 ⁵	24	36	48
Study Week	196	200	204	208	212	216	228	240
Medical history								X
Physical exam								X
Clinical evaluation (limited)	X	X	X	X	X	X	X	
Assessment of AE, concomitant meds	X	X	X	X	X	X	X	X
Questionnaires (QOL, Depression assessment, Fatigue questionnaire, and Health behavior)								X
Symptom questionnaire	X	X	X	X	X	X	X	X
CBC including platelets								X
Hepatic panel (AST, ALT, total bilirubin, direct bilirubin)	X	X	X	X	X	X	X	X
Other liver tests (ALKP, total protein, and albumin)	X	X	X	X	X	X	X	X
Renal Panel (Creatinine, calculated CrCl, BUN, Ca, PO₄)**	X	X	X	X	X	X	X	X
Urinalysis								X
PT/INR	X	X	X			X		X
Serum/plasma banking¹	X	X	X			X	X	X
HBeAg						X		X
Anti-HBe²						X		X
Anti-HBs²								X
HBsAg						X		X
HBsAg quant	X	X	X			X	X	X
HBeAg quant³				X		X	X	X
Quant HBV DNA	X	X	X			X	X	X
Antiviral drug resistance testing								X
Ultrasound exam⁴								X
Fibroscan (if available)								X ⁶

*Schedule is used for participants:

- (i) Those who meet criteria for stopping treatment at week 192 regardless of whether they stop treatment
- (ii) Those who stopped treatment early due to meeting criteria for treatment failure (non-response, partial response, virologic breakthrough);
- (iii) Those stopping treatment early due to an adverse event
- (iv) For those not eligible to stop treatment, visits only occur at study weeks 204, 216, 228, and 240

** Renal panel should be obtained at each study visit for participants who are on treatment. All participants should have creatinine tested at week 240

¹16mL of serum and 8mL of plasma at week 12, 24 and 48, 8mL of serum and 8mL of plasma at other time points

²Anti-HBe/Anti-HBs to be done at next visit if HBeAg/HBsAg becomes negative.

³In participants who are HBeAg positive in qualitative assay

⁴If clinically indicated, per AASLD guidelines, done as standard of care

⁵A hepatic panel and telephone follow-up (minimal assessment) may replace an outpatient visit if ALT at the preceding visit is <300 U/L for males or <200 U/L females and bilirubin is normal (total bilirubin <1.5 mg/dL or direct bilirubin <0.5 mg/dL)

⁶Fibroscan (if available) to be performed at week 240 if obtained at week 180 or 192 visits.

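### Section 7.3.d words the creatinine criterion for permanently stopping tenofovir DF as a rise of 1.2 mg/dL, whereas section 7.3.b treats 1.2 mg/dL as a level

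*Combined protocol and SAP*

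**What the plan says.** Two sections of the protocol give a creatinine rule for stopping treatment.

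- **Section 7.3.d** (discontinuation for selected biochemical abnormalities) opens "Tenofovir DF will be permanently discontinued and the participant considered a treatment failure" and then lists the qualifying findings. The creatinine item is "otherwise unexplained serum creatinine elevations by" ≥1.2 mg/dL and ≥0.5 mg/dL above baseline, on two occasions running. A calculated clearance below 30 mL/min is a separate item in the same list.
- **Section 7.3.b** (renal function) acts when creatinine is ≥1.2 mg/dL and >0.5 mg/dL "above baseline on two consecutive occasions, the study drugs will be discontinued". Drugs are not restarted unless another, reversible cause is found.

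The sentence just before the 7.3.b stopping rule, on additional testing, keeps level and rise apart: "If Cr increases to" ≥1.2 mg/dL and *by* ≥0.3 mg/dL from baseline. For a rise of 0.5 mg/dL or more, 7.3.b also provides that "repeat testing within 72 hrs will be performed and drug continued unless the study physician considers drug discontinuation necessary".

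No other text reconciles the two stopping rules.

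**The concern.** The two sections use the same pair of numbers and the same two-occasion confirmation, and both except rises that have another explanation. They look like one rule stated twice. In 7.3.b the 1.2 mg/dL is a floor on the creatinine value itself. In 7.3.d the preposition turns it into a change from baseline. That makes the 0.5 mg/dL clause idle and raises the threshold.

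This is operative renal-safety text for a drug given for 192 weeks, and section 5.2.3 acknowledges its renal tubular toxicity. Section 7.3.d is headed as the discontinuation rule, so site staff may look there first. It is also the only one of the two sections that attaches the treatment-failure label to a creatinine rise. A participant stopped correctly under 7.3.b may therefore fall outside the creatinine wording that carries the label.

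**Working it through.** The plan gives no figure to reproduce here. The check is one of logic and thresholds.

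**Inputs.** The criteria are those of 7.3.b and 7.3.d. Baseline creatinine *b* is assumed, because the documents give no distribution. Creatinine *C* moves in steps of 0.1 mg/dL. Each criterion must be met twice in a row, which is common to both sections and does not affect the comparison.

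**Step 1: is the 0.5 clause idle?** Literal 7.3.d requires C − b ≥ 1.2 and C − b ≥ 0.5. The first condition implies the second for every *b* and *C*. A check of all grid pairs found no case in which dropping the 0.5 clause changes the decision. With 1.2 as a level (C ≥ 1.2 and C − b ≥ 0.5), the clause does change decisions.

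**Step 2: where does each rule first act?**

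- 7.3.b: C ≥ 1.2 and C − b > 0.5, so the first grid value is max(1.2, b + 0.6).
- 7.3.d, literal: b + 1.2.
- 7.3.d with 'to' in place of 'by', keeping its ≥ sign: max(1.2, b + 0.5).

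| Assumed baseline (mg/dL) | 7.3.b | 7.3.d literal | Gap | 7.3.d with 'to' |
|---|---|---|---|---|
| 0.5 | 1.2 | 1.7 | 0.5 | 1.2 |
| 0.6 | 1.2 | 1.8 | 0.6 | 1.2 |
| 0.8 | 1.4 | 2.0 | 0.6 | 1.3 |
| 1.0 | 1.6 | 2.2 | 0.6 | 1.5 |
| 1.2 | 1.8 | 2.4 | 0.6 | 1.7 |

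From baseline 0.6 upward the gap is (b + 1.2) − (b + 0.6) = 0.6. The step size matters slightly. In 0.01 mg/dL steps at baseline 0.80, the two rules act at 1.31 and 2.00, a gap of 0.69.

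**Step 3: one participant.** Take baseline 1.0 and a confirmed, unexplained creatinine of 1.7, a rise of 0.7. Under 7.3.b, 1.7 ≥ 1.2 and 0.7 > 0.5, so drugs stop. Under literal 7.3.d, 0.7 < 1.2, so the creatinine criterion is not met. With 'to', it is met.

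**Step 4: do the rules collide?** If C − b ≥ 1.2, then C exceeds 1.2 for any positive baseline and the rise exceeds 0.5. Everyone who meets literal 7.3.d therefore already meets 7.3.b. The literal rule is nested inside the stricter one, and a site can obey both.

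**Step 5: the sign at 0.5.** After the wording change, the only difference left is ≥ in 7.3.d against > in 7.3.b. On this grid it is worth 0.1 mg/dL at baselines of 0.7 and above, and nothing at 0.6 or below.

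**The case against.** The strongest reply is that nothing goes wrong in practice. Section 7.3.b is mandatory and stricter, no text tells sites to use 7.3.d alone, and nothing in 7.3.d tells them to continue drug below its threshold. Its closing sentence on dose adjustment covers only renal insufficiency that does not require discontinuation. The idle clause itself hints that 1.2 was meant as a level. Other safeguards exist: the 72-hour retest with physician discretion, a renal panel at every on-treatment visit from week 12 (section 6.4), 48-hourly dosing at confirmed clearance of 30 to 50 mL/min, and a permanent stop below 30. All of this stands and limits the consequence. It does not make the sentence in 7.3.d correct.

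A fair caution also applies to the sign at 0.5. Comparison symbols can be altered when a document is converted, so that difference should be confirmed against the source file. The word 'by' cannot be explained that way.

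Three stronger readings are tempting, and the documents do not support them.

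- *That section 9.1 proves 'to' was meant.* Section 9.1 counts a "persistent increase in serum creatinine >1.0 mg/dL above baseline on two successive visits 4 weeks apart" toward stopping the whole study, so a rise of 1.1 is a case there yet misses literal 7.3.d. But 9.1 is a trial-level incidence rule with its own threshold and visit spacing. It need not be ordered against an individual stopping rule. The evidence for 'to' is the wording of 7.3.b and the idle clause.
- *That the delay can be stated as lost clearance.* The protocol names the MDRD method but gives no equation, so the gap is left in mg/dL.
- *That a treatment-failure endpoint is distorted.* Section 2.2.7 defines that endpoint as "Cumulative rates of primary nonresponse, partial virologic response and confirmed virologic breakthrough", and Appendix 4 likewise refers to "Those who stopped treatment early due to meeting criteria for treatment failure (non-response, partial response, virologic breakthrough". Both are virologic, and creatinine does not enter.

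**Conclusion.** The point holds as an error of wording in an individual safety threshold. Section 7.3.d makes its own 0.5 mg/dL clause redundant and is inconsistent with 7.3.b on whether 1.2 mg/dL is a rise or a level. 'Contradicts' would be too strong, because both rules can be followed together and the stricter one then governs.

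The size is a gap of 0.6 mg/dL between the two thresholds, on a 0.1 mg/dL grid and at assumed baselines of 0.6 to 1.2 mg/dL. That gap becomes late stopping only for a participant managed under 7.3.d alone. When both sections are applied, 7.3.b sets the stopping point, and with it any contribution to the adverse-event discontinuation rate in section 2.2.8. The primary analysis and the virologic failure endpoint do not depend on the wording. The correction should be made, but its weight is modest.

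**What to change.** In section 7.3.d, change 'by' to 'to' before the 1.2 mg/dL figure, so that the criterion reads as a level of ≥1.2 mg/dL together with a rise of 0.5 mg/dL above baseline, confirmed as now.

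Use the same inequality sign at 0.5 mg/dL in 7.3.b and 7.3.d. Either is consistent. Choosing > keeps the mandatory 7.3.b rule as it is, and a rise of exactly 0.5 still prompts the 72-hour retest. Choosing ≥ acts 0.1 mg/dL earlier on the grid above at baselines of 0.7 and over.

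Leave the scope of each section alone: 7.3.d is permanent and for unexplained rises, while 7.3.b allows resumption when another cause is identified. Leave the study-wide rule in 9.1 alone too.

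The cost is one word and one sign. Sample size, endpoints and the primary analysis are untouched.
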